10.8.2 Pregnancies

The investigator and each subject will determine the appropriate method of contraception for the subject during the participation in the study.

Male Subjects with Partners Who Become Pregnant

- The investigator will attempt to collect pregnancy information on any male subject’s female partner who becomes pregnant while the male subject is in this study. This applies only to male subjects who receive study product.
- After obtaining the necessary signed informed consent from the pregnant female partner directly, the investigator will record pregnancy information on the appropriate form and submit it to the sponsor within 24 hours of learning of the partner’s pregnancy. The female partner will also be followed to determine the outcome of the pregnancy. Information on the status of the mother and child will be forwarded to the sponsor. Generally, the follow-up will be no longer than 6 to 8 weeks following the estimated delivery date. Any termination of the pregnancy will be reported regardless of fetal status (presence or absence of anomalies) or indication for the procedure.

Female Subjects Who Become Pregnant

- The investigator will collect pregnancy information on any female subject who becomes pregnant while participating in this study. Information will be recorded on the appropriate form and submitted to the sponsor within 24 hours of learning of a subject’s pregnancy. The participant will be followed to determine the outcome of the pregnancy. The investigator will collect follow-up information on the subject and the neonate, and the information will be forwarded to the sponsor. Generally, follow-up will not be required for longer than 6 to 8 weeks beyond the estimated delivery date. Any termination of pregnancy will be reported, regardless of fetal status (presence or absence of anomalies) or indication for the procedure.
- While pregnancy itself is not considered to be an AE or SAE, any pregnancy complication will be reported as an AE or SAE. A spontaneous or elective abortion is always considered to be an SAE and will be reported as such. Any poststudy pregnancy-related SAE considered reasonably related to the study intervention by the investigator will be reported to the sponsor as described in Section 8.3.4. While the

investigator is not obligated to actively seek this information in former study subjects, he or she may learn of an SAE through spontaneous reporting.

10.9 Serious Adverse Event Reporting

10.9.1 Reporting Requirements

Any SAE occurring during the study period (beginning with informed consent) and through 30 days after study exit must be reported within 24 hours to Allergan on 2 SAE forms. The drug, and device SAE forms must be recorded and e-mailed per this protocol section (including to the SkinMedica Safety Contact below from V7 to V12). All subjects with an SAE must be followed up and the outcomes reported.

The principal investigator must supply Allergan and the REB with any additional requested information (eg, hospital discharge summary, autopsy reports and terminal medical reports) only upon request. Allergan will evaluate all SAEs for both drug and device. Device SAEs will be documented in writing as to whether they meet the definition of an USADE. These will be reported to all participating investigators, the regulatory authorities, and the REB.

[figure not shown]
In the event of an SAE, the investigator must:

1. Notify Allergan immediately (within 24 hours) using the SAE reporting forms. Emergency phone numbers and relevant Allergan personnel contacts are below.
2. Obtain and maintain in his/her files of all pertinent medical records, information, and medical judgments from colleagues who assisted in the treatment and follow-up of the subject.
3. Provide Allergan with a complete, written case history (AE report form), including copies of supporting reports (eg, progress notes, laboratory reports), upon request and a statement from the investigator as to whether the event was or was not related to the use of the investigational drug or device.
4. Promptly inform the governing REB of the SAE, if it is device-related, as required by the REB, local regulations, and the governing health authorities.

11.1 General Statistical Considerations

A brief summary of the general statistical analysis methods is provided below; full details will be provided in a separate statistical analysis plan (SAP), which will be finalized prior to database lock.

Data will be summarized using descriptive statistics (number of observations [n], mean, standard deviation, median, minimum, and maximum for continuous variables; and n and percent for categorical variables).

Hypothesis testing will be performed at a 0.05 significance level (2-sided). In this study, BELKYRA and without BELKYRA is the major treatment difference between enrolled subjects. Hence, unless specified, all endpoints will be summarized by those two groups (BELKYRA and without BELKYRA) and overall respectively. However, this study is not designed to compare the efficacy and safety outcomes between subjects treated with BELKYRA and those treated without BELKYRA. All discussion and interpretation related to study outcomes will be mainly focused on the overall results.

Two critical time points, baseline and end of study, will be referenced in most of statistical analyses for this study. Baseline is defined as the latest assessment prior to any study treatments for each subject. End of study is the last clinical visit an enrolled subject has in this study. For BELKYRA subjects who complete this study, the final visit will be their V12 visit; for subjects who will not be treated with BELKYRA, this visit will also be the V12 visit after approximately 5 months of treatment. Subjects who discontinue will be asked to return for the last clinical visit for end-of-study data collection.

11.1.1 Analysis Populations

The following analysis populations will be used:

- Full Analysis Population – all subjects who have met all eligibility criteria at the screening visit (V0) and received any product used as treatment in this study.
- Safety Population – defined the same as Full Analysis Population.
- Evaluable Population – all subjects as defined in the Safety Population who have had at least one post-treatment efficacy assessment at the final visit (V12).

The Full Analysis Population will be used for subject disposition, demographics and baseline characteristics summary, and the Safety Population will be used for safety analyses. The Evaluable Population will be used on key efficacy endpoints.

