
Three analysis populations are defined in Section 11. Unless otherwise specified in the SAP, efficacy analyses will be based on the Evaluable Population, safety analyses will be based on the Safety Analysis Population, and all other analyses will be based on the Full Analysis Population

[figure not shown]
Primary Efficacy Analysis

The primary efficacy endpoint is the change from baseline to the final visit in the overall Rasch-transformed scores of the FACE-Q Satisfaction with Facial Appearance Scale. This will be analyzed using paired t-test (or Wilcoxon signed-rank test if normality assumptions are not met).

6.2.3.1	Visit V9 (Juvéderm HA Facial Fillers and SkinMedica as Applicable)	37
6.2.3.2	Visit V10 (BOTOX Cosmetic and SkinMedica as Applicable)	37
6.2.3.3	Visit V11 (BOTOX Cosmetic and SkinMedica as Applicable)	37
6.2.3.4	Visit V12 (Final Study Visit/Early Termination)	38
6.2.4	Unscheduled/Missed Visits.....	38
6.2.5	Restrictions and Precautions	38
6.2.5.1	Prohibited Medications and/or Treatments	38
6.2.5.2	Special Diet or Activities	39
7	METHODS OF ASSESSMENT AND ENDPOINTS.....	40
7.1	Demographic Data	40
7.2	Medical History	40
7.3	Concomitant Medications	40
7.4	Pregnancy.....	40
7.5	Clinical Scales for Treatment Inclusion Only.....	40
7.6	Efficacy Endpoint Measurements	41
7.6.1	FACE-Q	41
7.6.2	Self-Perception of Age Questionnaire	41
7.6.3	Global Aesthetic Improvement Scale	41
7.6.4	Periorbital Aesthetic Appearance Questionnaire	41
8	DISCONTINUATION CRITERIA	43
8.1	Early Discontinuation of the Study.....	43
8.2	Early Discontinuation of Individual Subjects	43
9	TREATMENTS	45
9.1	Rescue Medications and Concomitant Treatments.....	45
9.2	Treatment Compliance.....	45
10	ADVERSE EVENTS.....	46
10.1	Drug	46
10.2	Medical Device	46
10.3	Injection Site Reactions	46
10.4	Unusual Failure in Efficacy	47
10.5	Serious Adverse Events	47
10.6	Unanticipated Serious Adverse Device Effects	48
10.7	Assessment of Adverse Events	48

10.7.1	Severity	48
10.7.2	Relationship to Study Product	49
10.8	Adverse Events and Pregnancy.....	49
10.8.1	Adverse Event Follow-up	50
10.8.2	Pregnancies	50
10.9	Serious Adverse Event Reporting.....	51
10.9.1	Reporting Requirements	51
10.9.2	Serious Adverse Event Contact Information	51
11	STATISTICAL METHODS.....	53
11.1	General Statistical Considerations	53
11.1.1	Analysis Populations.....	53
11.1.2	Subgroups	53
11.2	Demographics and Baseline Characteristics	54
11.3	Exposure and Concomitant Therapies	54
11.4	Efficacy Analyses	54

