6 PATIENT POPULATIONS

6.1 Full Analysis Populations

Full analysis population is defined as all subjects who have met all eligibility criteria at the screening visit (V0) and received any product used as treatment in this study.

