7 SUBJECT DISPOSITION

The number and percentage of subjects of the Full Analysis Population will be summarized by treatment group and overall. The number and percentage of patients for the following categories will be displayed:

- Enrolled
- Treated
 - BELKYRA
 - Non-BELKYRA
- Completed the Study
 - Yes
 - No
- Primary Reason for Discontinuation:
 - Adverse Event
 - Termination by Investigator/Sponsor
 - Lost to Follow-Up
 - Personal Reasons
 - Protocol Violation
 - Other

Screen-failure patients (i.e., patients screened but not treated) and the associated reasons for failure to enroll will be tabulated overall for the all screened patients. The number and percentage of patients who complete the V12 and of patients who prematurely discontinue during the same period will be presented for each treatment group and pooled across treatment groups for the Full Analysis Population. The reasons for premature discontinuation from the V12 as recorded on the termination pages of the electronic case report forms will be summarized (number and percentage) by treatment group for the Full Analysis Population. All patients who prematurely discontinue during the V12 will be listed by discontinuation reason for the Full Analysis Population.

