11 SAFETY ANALYSES

The safety analysis will be performed using the Full Analysis Population. The safety parameters will include adverse events (AEs). The last nonmissing safety assessment before the first dose of study treatment will be used as the baseline for all analyses of that safety parameter.

Categorical variables will be summarized by number and percentage of patients. No statistical test will be performed.

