For the summary of number of events, if a subject experiences more than one event within the same SOC and PT, all events will be counted.

All AEs will be listed, and additional listings will be presented for AEs leading to discontinuation, serious AEs and AEs resulted in deaths.

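### The safety population excludes treated subjects who did not meet every eligibility criterion at V0, so the adverse event tables need not cover everyone exposed

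*Protocol*

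**What the plan says.** Protocol 11.1.1 admits a subject to the Full Analysis Population on two joint conditions: "all subjects who have met all eligibility criteria at the screening visit (V0) and received any product used as treatment in this study". The Safety Population is "defined the same as Full Analysis Population", and the same section assigns it to the safety analyses. SAP 6.1 repeats the two conditions. The SAP has no separate safety set; its section 11 states: "The safety analysis will be performed using the Full Analysis Population". The summary tables of treatment-emergent events in SAP 11.1 come under that sentence.

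Other summaries rest on the same set. The disposition table in SAP 7 reports "The number and percentage of subjects of the Full Analysis Population". SAP 9 names no population for exposure, so the default in the protocol synopsis (Statistical Methods) applies: "all other analyses will be based on the Full Analysis Population". SAP 7 restricts screen failures to patients who were screened and not treated. On listings, SAP 11.1 says "All AEs will be listed" and does not restate a population.

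**The concern.** A safety set should contain everyone exposed to the products. Here membership also depends on eligibility at V0. Protocol 5 allows treatment only for eligible subjects, and protocol 6.1 gives enrolment numbers only to subjects who meet all criteria. If those controls hold, the eligibility condition adds nothing. If one fails, the only thing the condition can do is remove a person who was treated.

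The subjects removed are not a random selection. Several criteria are safety screens, such as conditions that raise the risk from botulinum toxin, a history of facial nerve palsy, and hypersensitivity to hyaluronic acid or lidocaine. A subject treated despite one of these is someone whose events the tables most need to show. At stake are the counts and rates of adverse events, the number reported as treated, and agreement between tables and listings.

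**Working it through.** The plan states no figure to reproduce, because the point rests on set definitions. I traced the definitions first and then sized the effect.

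**Tracing one subject.** Take a subject who received an injection and is then found to have failed a criterion that was fixed at V0, for example BMI over 30, filler within the previous 12 months, toxin within the previous 6 months, or a history of facial nerve palsy.

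- Adverse event tables (SAP 11.1): run on the Full Analysis Population (SAP 11), which requires eligibility at V0 (SAP 6.1). The subject is out of numerator and denominator.
- Disposition (SAP 7): based on the same set. The subject is missing from the treated row. If withdrawn for the deviation, the subject is also missing from the protocol-violation row.
- Exposure (SAP 9, with the synopsis default): out.
- Screen failures (SAP 7): out, because the subject was treated.
- Listings (SAP 11.1): all events are to be listed with no population named, so the events may appear there.
- Recording and expedited reporting (protocol 10 and 10.9.1): unaffected.

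A subject who was eligible at V0 and meets an exclusion later stays in the set.

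**Size.** Let N be the number treated, k the number treated but ineligible at V0, x the number of treated subjects with an event, and e the number of those x who are among the k. The rate among all treated is x/N. The planned table shows (x − e)/(N − k).

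Inputs: N = 60, with about 20 treated with BELKYRA and 40 without (protocol 4.1 and 11.6). The values of k, x and e are assumed.

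Denominators for k = 1, 3 and 6 are 60 − k = 59, 57 and 54. They leave out 1/60 = 1.7%, 3/60 = 5% and 6/60 = 10% of treated subjects.

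Now let k = 1, x = 1 and e = 1: a single serious event, in the ineligible subject. The intervals are exact (Clopper-Pearson) 95%. With no events the upper limit is 1 − 0.025^(1/n). With one event the lower limit is 1 − 0.975^(1/n), and the upper limit solves (1 − p)^n + n·p·(1 − p)^(n−1) = 0.025.

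| Group | All treated | Planned table |
|---|---|---|
| Overall | 1/60 = 1.67% (0.04 to 8.94) | 0/59 = 0% (0 to 6.06) |
| BELKYRA | 1/20 = 5.00% (0.13 to 24.87) | 0/19 = 0% (0 to 17.65) |
| Without BELKYRA | 1/40 = 2.50% (0.06 to 13.16) | 0/39 = 0% (0 to 9.03) |

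Each group row supposes that the excluded subject belonged to that group.

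With a commoner event, x = 6, k = 3 and e = 3, the rate among all treated is 6/60 = 10.0% and the table shows 3/57 = 5.3%. If the excluded subject had no event (x = 6, k = 1, e = 0), only the denominator moves: 6/59 = 10.2% against 10.0%. If k = 0, nothing changes.

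**The case against.** The strongest reply is that the condition can be read as meeting the criteria as judged at V0, which would simply separate subjects cleared for treatment from screen failures. On that reading a subject cleared in error stays in, and neither document describes a retrospective review that would reclassify anyone. But the text does not say this. It requires the criteria to have been met. If the milder reading was intended, the condition is redundant for treated subjects and nothing is lost by removing it.

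A second reply is that the excluded group is empty by design. The documents themselves allow for failures: protocol 9.2 has monitors review compliance with eligibility criteria, and protocol 8.2 lists a protocol violation and a met exclusion criterion as reasons for discontinuation. It remains true that the number affected is unknown and may be zero.

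Three further points stand. The illustration is an unfavourable case, because it places the only event in the excluded subject. Safety is summarised without testing and is not a stated objective. A mismatch between tables and listings is possible but not certain: the listing sentence falls within the section that opens by naming the Full Analysis Population. If the listings follow that population, the events would be missing from both.

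**Conclusion.** The concern holds. The protocol and SAP agree with each other, and as written a treated subject who had not met a criterion at V0 is left out of the adverse event tables, the disposition table and the exposure summary, and is counted nowhere else. The effect is conditional on at least one such subject, and the documents give no basis for estimating how many. In a study of 60, with about 20 in the BELKYRA group, one subject can decide whether a serious event appears in the summary tables at all: 1/60 against 0/59 overall, or 1/20 against 0/19, assuming that subject has the only such event. No hypothesis test and no efficacy result is affected. This should be corrected, but it does not threaten the primary analysis.

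**What to change.** In protocol 11.1.1, define the Safety Population as all subjects who received any study product, regardless of eligibility. Add the same definition to SAP 6 and name that population in SAP 11. Use it for the adverse event, exposure and disposition summaries, state that the adverse event listings cover it, and add a listing of V0 eligibility deviations.

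The membership of the Evaluable Population need not change. Protocol 11.1.1 currently builds it on the Safety Population, so there it should be reworded to start from the Full Analysis Population, as SAP 6.2 already does. This leaves the primary analysis untouched.

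The sentences that assign populations need matching edits: the synopsis default, protocol 11.1.1, and SAP 6.2, 7, 9 and 11. Demographics are now on the Full Analysis Population. Either move them to the Safety Population or show both counts, so that a difference in denominators is explained.

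The cost is one definition in each document, these consequential edits and one listing, with no new data. The drawback is that any ineligible subjects who were treated will enter the safety tables, which is what those tables are for.

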11.1.2 Subgroups

Two subgroups will be examined separately:

- Gender: As male and female subjects may have differing expectations/perceptions of aesthetic improvement, they will be examined separately.
- BELKYRA: As it is expected that approximately two-thirds of the enrolled population will not be treated with BELKYRA, subjects treated and not treated with BELKYRA will be examined separately.

Additional subgroup analysis will be discussed in the SAP.

11.2 Demographics and Baseline Characteristics

Subject disposition, demographics and baseline characteristics will be summarized using descriptive statistics.

11.3 Exposure and Concomitant Therapies

Subject study product exposure and compliance will be summarized using descriptive statistics for each product, combination of multiple products, and overall exposure respectively.

The latest version of the *World Health Organization Drug Dictionary* will be used to classify prior and concomitant medications and therapies by therapeutic class and drug/device name. Prior medication/therapy is defined as those started by enrolled subjects before the date of first study treatment. Concomitant medication/therapy is defined as those taken on or after the date of first treatment. Prior and concomitant medications/therapies will be summarized using descriptive statistics.

11.4 Efficacy Analyses

Unless stated otherwise, all efficacy analyses will compare post-treatment assessment values to the subject's corresponding baseline assessment value, and will be based on the Evaluable Population.

11.4.1 Primary Efficacy Analysis

The primary efficacy endpoint is the change from baseline to the final visit (V12) in the overall Rasch-transformed scores of the FACE-Q Satisfaction with Facial Appearance Scale. This will be analyzed using paired t-test (or Wilcoxon signed-rank test if normality assumptions are not met).

11.4.3 Missing Data

Missing data strategy will be documented in the SAP.

11.4.4 Adverse Events

Device-related AEs will be captured with TrackWise Enterprise Quality Management Software and coded using AE term codes. Treatment-emergent AEs will also be summarized by serious AEs (SAEs), AE severity, AE leading to treatment or study early termination, and relationship to study drugs/devices. SAEs will be coded using MedDRA version 17.0 or higher, and presented by system organ class and preferred term.

11.5 Interim Analyses and Data Monitoring

No formal interim analyses are planned for this study.

11.6 Determination of Sample Size

A sample size of 48 subjects will provide 90% power to detect whether change from baseline to end-of-study visit in the FACE-Q Satisfaction with Facial Appearance Overall Scale Rasch-transformed score is different from zero, assuming a mean change of 12.0 and a standard deviation of 20.0. This calculation is based on a 1-sample, 2-sided t-test at 5% significance level. The assumptions of mean and standard deviation are based on FACE-Q results from Allergan HARMONY Study GMA-CMB-14-001. With a 20% drop-out rate (for early withdrawals and/or subjects who failed to duly complete the FACE-Q Satisfaction with Facial Appearance Overall Scale assessment at end of study), 60 subjects will be enrolled. From the 60 subjects planned to enroll in this study, approximately 20 subjects will be treated with BELKYRA.

PASS 2008 software was used to calculate the sample size.

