14 DETERMINATION OF SAMPLE SIZE

A sample size of 48 subjects will provide 90% power to detect whether change from baseline to end-of-study visit in the FACE-Q Satisfaction with Facial Appearance Overall Scale Rasch-transformed score is different from zero, assuming a mean change of 12.0 and a standard deviation of 20.0. This calculation is based on a 1-sample, 2-sided t-test at 5% significance level. The assumptions of mean and standard deviation are based on FACE-Q results from Allergan HARMONY Study GMA-CMB-14-001. With a 20% drop-out rate (for early withdrawals and/or subjects who failed to duly complete the FACE-Q Satisfaction with Facial Appearance Overall Scale assessment at end of study), 60 subjects will be enrolled. From the 60 subjects planned to enroll in this study, approximately 20 subjects will be treated with BELKYRA.

Subjects will be assigned to study treatment only if they meet the inclusion criteria and none of the exclusion criteria. Subjects who discontinue treatment will not be replaced.

EXACT software (version 6) was used to confirm the sample size in the protocol.

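### The stated 90% power does not follow from the stated inputs: 48 subjects with mean change 12.0 and SD 20.0 give 98.3%, and 90% needs only 32 evaluable subjects

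*Protocol*

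**What the plan says.** Protocol 11.6 gives a complete set of inputs. The claim is "A sample size of 48 subjects will provide 90% power to detect whether change from baseline to end-of-study visit" in the Rasch-transformed FACE-Q Satisfaction with Facial Appearance Overall score, "assuming a mean change of 12.0 and a standard deviation of 20.0". On the test it says "This calculation is based on a 1-sample, 2-sided t-test at 5% significance level". On the origin of the inputs it says "The assumptions of mean and standard deviation are based on FACE-Q results from Allergan HARMONY Study GMA-CMB-14-001", but it does not show that study's figures. A 20% drop-out allowance then takes 48 to 60 enrolled. The protocol names PASS 2008 as the program used.

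SAP 14 repeats the same n, power, mean, SD, test and drop-out rate, and adds "EXACT software (version 6) was used to confirm the sample size in the protocol". It also says "Subjects who discontinue treatment will not be replaced".

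The planned primary analysis (protocol 11.4.1) matches the test used for sizing, with a rank-based fallback: "This will be analyzed using paired t-test (or Wilcoxon signed-rank test if normality assumptions are not met". SAP 18 records no change from the protocol's analyses.

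**The concern.** The printed mean and SD give a standardised effect of 12.0/20.0 = 0.6. For a one-sample t-test that is a large effect, and 48 subjects is well above what 90% power would normally require. All the inputs are printed, so the statement can be checked directly.

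Two things are at stake. First, the trial size rests on this one sentence, and a reader cannot reproduce it from either document. Second, the margin for loss depends on which figure is wrong. Subjects who discontinue treatment are not replaced, and the primary analysis uses only subjects with a V12 efficacy assessment. How much loss the trial can absorb is therefore a practical question.

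**Working it through.** **Inputs** (protocol 11.6, repeated in SAP 14): n = 48 evaluable; mean change 12.0; SD 20.0; one-sample t-test, two-sided, alpha 0.05; drop-out 20%; stated power 90%.

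**Method.** Exact power from the noncentral t distribution with n − 1 degrees of freedom and noncentrality (mean/SD) × √n.

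**The plan's own figure.** At n = 48 the noncentrality is 0.6 × √48 = 4.157 and the two-sided 5% critical value on 47 degrees of freedom is 2.012. Power is 98.26%. A normal approximation gives 98.60%, and a simulation of 200,000 trials gives 98.26%. The stated 90% is not reproduced; the gap is about 8 percentage points.

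**Sample size for 90% on the printed inputs.**

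| Evaluable n | Power |
|---|---|
| 31 | 89.8% |
| 32 | 90.8% |
| 40 | 95.9% |
| 48 | 98.3% |
| 60 | 99.5% |

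The smallest n is 32, which is 32/(1 − 0.20) = 40 enrolled. The plan's drop-out step is itself correct: 48/(1 − 0.20) = 60.

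**Do variants close to the text explain 48?**

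- One-sided 5%: n = 26, further from 48.
- Signed-rank fallback: at an efficiency of 0.955 relative to the t-test, 32/0.955 = 33.5, so 34. At the lower bound of 0.864, 32/0.864 = 37.04, so at most 38.
- A different power target: 80%, 95% and 98% need 24, 39 and 47.

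None of these gives 48 for 90%.

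**What would have to differ for 90% at n = 48?** Each line changes one input and holds the others. These values were solved backwards from 48 and 90%. They are illustrations, and neither document states any of them.

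| Changed input | Value solving for 90% | Power at n = 48 at a nearby value |
|---|---|---|
| SD of change | 25.1 | SD 25: 90.3% |
| Mean change | 9.55 | mean 9.6: 90.3% |
| Alpha | 0.0067 | 0.05/7: 90.4% |
| SD 20 taken as the per-visit SD, with correlation r between visits | r = 0.21 | r = 0.20: 89.6%; r = 0.22: 90.3% |

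The last line uses SD of change = 20 × √(2(1 − r)). At r = 0.5 this equals 20, and the required n is again 32.

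**Margin for loss from 60 enrolled, keeping 90% power.** At SD 20: (60 − 32)/60 = 28/60 = 47%. At SD 25, where 48 are needed: (60 − 48)/60 = 12/60 = 20%, exactly the planned drop-out. With 40 evaluable subjects, power is 95.9% at SD 20 and 84.1% at SD 25.

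**The case against.** The strongest reply is that the error is conservative. On the printed inputs the trial has more power than it claims. The test, alpha, analysis population and enrolment of 60 do not depend on the power figure. All of that is true, and it is why this is a correction and not a challenge to the design.

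A second reply is that 90% may be a floor: 48 subjects do provide no less than 90%, and the number may have been chosen for other reasons. The text does not say so. It also fits poorly with the protocol's statement that software was used to calculate the sample size, because these inputs at 90% return 32. If a floor was meant, the plan should say so and give the reason for 48.

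A third reply is that the alternative explanations are speculative. That stands. A divided alpha contradicts the 5% level printed in both documents, and a per-visit SD contradicts applying the SD to a one-sample test of change. They show only that small unstated changes could produce 48, and that the loss margin would then differ. Because each was solved to give about 90%, they are not independent evidence that power is adequate.

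Finally, not reproducing the earlier study's figures is not an error in itself. It only means the reader cannot settle the matter from these documents. The same goes for the SAP's brief statement about the second program, which is missing detail.

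**Conclusion.** The concern holds. With a mean change of 12.0, an SD of change of 20.0 and a one-sample, two-sided 5% t-test, power at 48 evaluable subjects is 98.3%, not 90%, and 90% needs 32, not 48. The n, power, mean, SD and alpha printed in protocol 11.6 and SAP 14 do not form one consistent calculation, unless 90% was meant as a floor, which neither document says. The documents do not identify the figure at fault.

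The result assumes approximately normal changes; moving to the signed-rank test does not close the gap. The trial is not shown to be underpowered, and nothing here argues for enrolling fewer than 60. The point should be fixed because the error appears in both documents and the true margin for loss, 47% at SD 20 against 20% at SD 25, cannot be read from them.

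**What to change.** Retrieve the original software output and the mean and SD from the source study. Reconcile n, power, mean, SD and alpha in protocol 11.6 and SAP 14, and say explicitly whether the SD is that of the change or of the score at a visit.

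- If 12.0 and 20.0 stand, restate the power at 48 evaluable subjects as about 98%.
- If the original output used a different input, print that input.
- If 48 was chosen on other grounds and 90% was meant as a minimum, say so and give the grounds.

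In SAP 14, state what the second program confirmed (the number 48, the power, or both) and with which inputs.

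The cost is a short wording correction in each document once the output has been checked. Enrolment and analysis do not change.
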